8.1. Medical and Medication History

Medical and medication histories including any allergies will be recorded at screening, including, but not limited to, detailed histories on allergies [e.g. rhinitis, dermatitis, food, aspirin/non-steroidal anti-inflammatory drugs (NSAIDs) and asthma].

8.2. Demographics

Demographic data will be recorded at the Screening Visit

8.3. Height, Weight and Body Mass Index

Height and weight measurements will be recorded in compliance with hVIVO's standard procedures.

BMI will be calculated as: $BMI \text{ (kg/m}^2\text{)} = \frac{\text{Weight (kg)}}{\text{Height (m}}^2\text{)}$

8.4. Alcohol Breath Testing

Breath alcohol testing will be conducted to determine compliance with the study alcohol restrictions. Additional tests may be conducted for assessing eligibility at the discretion of the Investigator. Results will be recorded in the source documents.

8.5. Complete Physical Examination

A complete physical examination to include a full systemic assessment.

hVIVO template identifier: (G_0687) v3.0

8.6. Direct Physical Examination

Directed physical examinations will be conducted as deemed appropriate by the Investigator and will include examination of the ears, nose, throat and chest (via stethoscope).

Assessment and grading of any upper respiratory tract (URT) (nasal discharge, otitis, pharyngitis, sinus tenderness) and lower respiratory tract (LRT) symptoms (abnormal breath sounds externally [e.g. stridor] and on chest auscultation [wheezing or rhonchi, crepitations] will be performed. Physician-reported assessments of viral challenge related illness will be graded in accordance with their intensity and documented in the source data.

Following viral challenge, URT and LRT symptoms (as described above) will be expected and presumed to represent virus infection consequent to viral challenge and will not be additionally captured as AEs unless they meet the definition of an AE, and are deemed to be clinically significant (in the opinion of the Investigator) to be classed as AEs.

Following viral challenge all unexpected (in the opinion of the Investigator) directed physical examination findings will be captured as AEs, along with all other occurrences that meet the criteria for an AE.

8.7. Vital Signs

Vital signs assessments will be recorded as follows:

- Heart rate (HR) will be recorded in beats per minute.
- Respiratory rate (RR): respirations will be counted and recorded as breaths per minute.
- BP: systolic BP and diastolic BP will be measured in millimetres of mercury (mmHg); measurements will be made supine. Where possible, the same arm will be used for all measurements.
- Peripheral arterial oxygen saturation (SpO₂%) will be assessed using pulse oximetry.

In the event of a participant having an unexpected abnormal or out of normal range result, the assessment may be repeated after at least 2 minutes to exclude a technical fault and confirm the original reading. The assessment may then be repeated at the PI's discretion and in accordance with hVIVO's SOPs.

Study specific normal ranges are provided in [Appendix 10.4](#) If a result is out of the normal range and meets the criteria for an AE, the severity of the AE will be guided by the the United States Food and Drug Administration (FDA) Adult Toxicity Grading Scale for Preventive Vaccine Clinical Trials September 2007. Deterioration in a vital sign (compared to baseline) should only be reported as an AE if the deterioration fulfils the criteria for an AE. If deterioration in a vital sign is associated with clinical signs and symptoms, the sign or symptom will be reported as an AE and the associated vital sign will be considered as additional information.

8.8. Temperature

Body temperature will be measured by either oral or tympanic route. The study specific normal range for temperature is detailed in [Appendix 10.4](#). The severity of out of normal range values will be assigned using the FDA toxicity scale as a guide.

Temperature may be more frequently monitored in quarantine if appropriate.

Following viral challenge, pyrexia will be expected and presumed to represent virus infection consequent to viral challenge and will not be additionally captured as an AE unless it meets the definition of an AE, and is deemed to be clinically significant (in the opinion of the Investigator) to be classed as an AE.

Following viral challenge all unexpected (in the opinion of the Investigator) pyrexia will be captured as an AE, along with all other occurrences that meet the criteria for an AE.

Febrile illness (FI) is defined as any occurrence of temperature $\geq 37.9^{\circ}\text{C}$

Vaccine reactogenicity temperature monitoring will be recorded in the vaccine dairy card, as detailed in [Section 8.11.1](#).

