Nausea	Does not interfere with activity	Some interference with activity	Prevents daily routine activity	Emergency room visit or hospitalisation for severe nausea
Diarrhea	2 to 3 loose stools in 24 hours	4 to 5 loose stools in 24 hours	6 or more loose stools in 24 hours	Emergency room visit or hospitalisation for severe diarrhea
Muscle pain	Does not interfere with activity	Some interference with activity	Prevents daily routine activity	Emergency room visit or hospitalisation for severe muscle pain
Joint pain	Does not interfere with activity	Some interference with activity	Prevents daily routine activity	Emergency room visit or hospitalisation for severe joint pain

The highest temperature for each day for 7 days after vaccination is to be recorded in the VDC. For reporting purposes, fever will be analysed using the grading scale in Table 13.

Table 13 Grading Scale for Fever in the VDC

Mild Grade 1	Moderate Grade 2	Severe Grade 3	Grade 4
≥38.0°C to 38.4°C	>38.4°C to 38.9°C	>38.9°C to 40.0°C	>40.0°C

The presence or absence of each systemic event on a given day is defined as follows:

- = “Missing,” if the value is missing on a given day;
- = “Yes,” if the participant reports a temperature ≥38.0°C for fever **or** “Mild,” “Moderate,” “Severe,” or “Grade 4” for the remaining events on a given day;
- = “No,” if the participant reports a temperature <38.0°C for fever **or** “None” for the remaining events on a given day.

For each systemic event, the following variables will be derived:

1. Presence or absence of each systemic event on each day (Days 1-7) after vaccination.
2. Presence or absence of each systemic event on “any day (Day 1-7)” after vaccination.
3. Maximum severity of each systemic event on “any day (Day 1-7)” after vaccination.
4. Presence or absence of any systemic event on “any day (Day 1-7)” after vaccination.
5. Duration of each systemic event after vaccination.
6. Onset day of each systemic event after vaccination.
7. Onset day of any systemic event after vaccination.

The derivation of these variables is similar to the derivation of the variables for local reactions ([Section 10.3.13](#))

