10.4. Appendix 4: Normal Ranges

Vital signs normal ranges

Vital signs	Lower limit	Higher limit	Units
Tympanic temperature (above 37.8 classed as pyrexia)*	35.5	37.8	oC
Oxygen saturation	Normal is \geq 95		%
Respiratory rate	10	20	breaths per minute
Heart rate	40	100	beats per minute
Systolic BP	90	140	mmHg
Diastolic BP	60	90	mmHg

* Tympanic temperature refers to temperatures not recorded as part of the vaccine reactogenicity monitoring

ECG

ECG Parameters	Lower limit	Higher limit	Units
HR	40	100	bpm
QRS	60	120	ms
PR interval	120	220	ms
QT	320	450	ms
QTc	Normal for females is $<$ 450		ms
	Normal for males is $<$ 430		
QTcF	320	450	ms
QTcB	320	450	ms

Spirometry

Spirometry parameters	Lower limit	Higher limit	Units
FEV1	Normal if \geq 80% of the predicted value		litres
FEV1/FVC	Normal if \geq 70% (\geq 0.7) of the predicted value		litres

No single value should be used in isolation, all spirometry reference ranges require physician interpretation of the participant's overall status to determine their relevance.

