10.6.2. Study definition of infection and illness

TERM	CRITERIA
Seroconversion	Not applicable for RSV.

TERM	CRITERIA
Lower Respiratory Tract Illness (LRTI)	
Any one of the following signs and/or symptoms on two consecutive scheduled assessments, at least one of which must feature Grade 2 severity, or if any of the following attain Grade 3 severity once:
 
 ○ Self-reported symptoms: cough, shortness of breath, chest tightness and wheeze ○ Physician findings: Abnormal breath sounds externally (e.g. stridor, wheezing) and on chest auscultation (rhonchi, crepitations or other).
Upper Respiratory Tract Illness (URTI)	
Any one of the following signs and/or symptoms on two consecutive scheduled assessments, at least one of which must feature Grade 2 severity, or if any of the following attain Grade 3 severity once:
 
Self-reported symptoms: rhinorrhoea (runny nose), nasal congestion (stuffy nose), sore throat, sneezing.
 
Physician findings: nasal discharge, otitis, pharyngitis, sinus tenderness.

Systemic Illness	
Fulfils the criteria for febrile illness, or fulfils the definition of upper respiratory tract illness and/or lower respiratory tract illness
 
And
 
Any one of the following symptoms on two consecutive scheduled assessments, at least one of which must feature Grade 2 severity, or if any of the following attain Grade 3 severity once
 
 • malaise • headache • muscles and/or joint ache • chilliness • feverishness
Febrile Illness	Any occurrence of temperature $\geq 37.9^{\circ}\text{C}$
Viral shedding	
One or both of the following definitions must be met (between Day +2 and discharge from quarantine):
 
 • At least 2 positive quantifiable detections by viral load qPCR assay specific for the challenge virus, reported on 2 or more consecutive days and from 2 independent samples (which can either be the same type of sample or different e.g. throat swab and nasal wash or 2 nasal wash samples); • One positive detection by viral load qPCR assay, specific for the challenge virus, in which an aliquot of the same sample has also tested positive in a viral culture assay appropriate for detecting the challenge virus.

TERM	CRITERIA
Laboratory confirmed RSV infection	Viral shedding definition has been met.

11. References

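### Febrile illness counts any single reading of 37.9 °C or more, with no limit to scheduled readings and no fixed window, so sicker participants can have more chances to qualify

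*Combined protocol and SAP*

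**What the plan says.** Section 8.8 says "Febrile illness (FI) is defined as any occurrence of temperature" at or above 37.9 °C. Section 10.6.2 gives the same criterion: "Any occurrence of temperature" at or above that value. One reading is enough. Confirmation, scheduled timing and dates are not mentioned.

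Three other provisions bear on how many readings a participant has and how they are taken:

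- The Schedule of Activities sets temperature at three times daily in quarantine. Section 8.8 adds: "Temperature may be more frequently monitored in quarantine if appropriate". It gives no trigger and no cap.
- Sections 1.2 and 4.1 allow the stay to run past Day 12 when a participant still has clinically significant symptoms or detectable virus.
- On route, Section 8.8 says "Body temperature will be measured by either oral or tympanic route". Appendix 10.4 has one temperature line, "Tympanic temperature (above 37.8 classed as pyrexia", and its footnote applies that line to temperatures taken outside vaccine reactogenicity monitoring.

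Febrile illness is a tertiary endpoint under the objective on challenge-virus disease (Section 3). It is also one of the entry routes to Systemic Illness in Section 10.6.2, which additionally requires a qualifying systemic symptom. Under Section 9.6.7, tertiary endpoints are descriptive unless otherwise specified, with details left to the SAP.

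**The concern.** An endpoint met by one reading out of many becomes more likely as readings accumulate. Three readings a day are already scheduled, so the natural reason to take more is that someone is unwell. An extended stay for symptoms or virus works in the same direction. Blinding does not remove this, because the trigger is illness and not allocation.

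If the vaccine reduces illness, placebo participants would on average be measured more often. Part of any difference in febrile illness would then reflect the number of readings. The main route to upper and lower respiratory illness has some protection, since it needs a finding "on two consecutive scheduled assessments, at least one of which must feature Grade 2 severity". That protection is partial, because a single Grade 3 finding also qualifies. Febrile illness has no such condition.

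At stake is how far a descriptive difference in febrile illness, and to a lesser degree in Systemic Illness, can be read as reduced RSV disease.

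**Working it through.** **Is there a figure to reproduce?** The plan gives no rate, power or sample size for febrile illness. The illustration borrows the symptomatic-infection rates in Section 9.2, so these were checked first. A 60% reduction from 59.26% is 0.4 × 59.26% = 23.7%, as stated. The usual two-proportion formula (two-sided 5%, 80% power) is

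n = [1.96 √(2p̄(1−p̄)) + 0.8416 √(p₁(1−p₁) + p₂(1−p₂))]² / (p₁−p₂)².

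With p₁ = 0.5926, p₂ = 0.237 and p̄ = 0.4148 it gives 29 per arm. Power at the planned 31 per arm is 82.8%. The borrowed rates are consistent with the plan.

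**Inputs**

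- Scheduled post-challenge readings: 3 × 11 (Days 1 to 11) + 1 (Day 12) = 34. This is an assumption, because the schedule table is broken in the text.
- Share ill: 59.26% placebo and 23.7% vaccine (Section 9.2), used as a stand-in for those who would be measured more often.
- Chance q that one reading is 37.9 °C or more: assumed 0.1%, 0.5% or 1%, with readings independent.
- Extra readings m in ill participants only: assumed 6 or 24, from added monitoring or a longer stay.
- Arm size: 31 (Section 9.2).

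**Model A: the vaccine has no effect on fever, and q is the same in everyone.** The chance of at least one qualifying reading in k readings is f(k) = 1 − (1−q)^k.

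- Placebo = 0.5926 f(34+m) + 0.4074 f(34)
- Vaccine = 0.237 f(34+m) + 0.763 f(34)
- Difference = 0.3556 × [f(34+m) − f(34)]

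Example: for q = 0.5% and m = 24, f(34) = 15.67% and f(58) = 25.23%. The difference is 0.3556 × 9.56% = 3.4 points, or 31 × 0.034 = 1.05 cases.

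| q | m | Placebo | Vaccine | Apparent relative reduction | Excess placebo cases at 31 per arm |
|---|---|---|---|---|---|
| 0.1% | 6 | 3.7% | 3.5% | 5.6% | 0.1 |
| 0.1% | 24 | 4.7% | 3.9% | 17.3% | 0.3 |
| 0.5% | 6 | 17.2% | 16.3% | 5.2% | 0.3 |
| 0.5% | 24 | 21.3% | 17.9% | 15.9% | 1.1 |
| 1% | 6 | 31.4% | 29.9% | 4.7% | 0.5 |
| 1% | 24 | 38.0% | 32.6% | 14.3% | 1.7 |

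The difference formula shows two zeros. With scheduled readings only (m = 0) the difference is 0 for every q. With equal illness in the arms, the factor 0.3556 becomes 0 and the artefact disappears.

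**Model B: fever follows illness.** Ill participants have a chance r per reading, and the others 0.1%.

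| r | Relative reduction, m = 0 | m = 6 | m = 24 |
|---|---|---|---|
| 1% | 49.2% | 50.4% | 52.7% |
| 2% | 53.5% | 54.1% | 55.3% |
| 5% | 56.0% | 56.2% | 56.5% |

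The relative reduction hardly moves. The gap in case numbers still widens. At m = 24 it widens by 31 × (0.145 − 0.091) = 1.7 cases for r = 1%, 31 × (0.234 − 0.165) = 2.1 for 2%, and 31 × (0.326 − 0.282) = 1.4 for 5%. Here the extra readings are finding real fever more often in ill participants.

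**The case against.** The case against giving this much weight is strong, and most of it stands.

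- **The inflation is not shown.** The documents give no count of extra readings and no trigger for them. That they would go to people who feel ill is an inference. Repeats after a reading that already qualifies add no case. Paracetamol, permitted at the investigator's discretion (Section 6.5), could lower readings in ill participants and act the other way.
- **A large figure is easy to produce.** Doubling the readings (34 extra) in every symptomatic participant at q = 0.5% gives 23.5% against 18.8%, an apparent 20% reduction. But symptomatic infection can be met by Grade 1 symptoms in two categories, and the calculation assumes that fever is unrelated to illness. The documents support neither assumption, so 20% should not be quoted as the size of the problem.
- **The consequence is limited.** The endpoint is tertiary and descriptive. Febrile illness alone does not make Systemic Illness.

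A reader might also infer four further points that the documents do not support:

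- *That 37.9 °C contradicts a 38.0 °C oral fever limit.* The statement "fever will be analysed using the grading scale in Table 13" concerns the vaccination diary only. Outside reactogenicity monitoring, Appendix 10.4 puts pyrexia above 37.8 °C, which matches 37.9 °C.
- *That having two routes favours one arm.* Route applies to both blinded arms. It can add misclassification but creates no stated imbalance.
- *That readings before challenge count.* The wording has no start date, but the objective is challenge-virus disease, so that reading is strained.
- *That "Directed physical examinations will be conducted as deemed appropriate by the Investigator" (Section 8.6) leaves respiratory illness similarly open.* The Schedule of Activities sets those examinations in quarantine, and Section 8 requires adherence to it.

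What remains is that the definition, as written, counts unscheduled readings and readings during an extended stay.

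**Conclusion.** The gap is real and minor. As written, participants who are more ill can have more opportunities to meet febrile illness, so a true vaccine effect on illness can be modestly exaggerated on this endpoint.

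With a common chance per reading of 0.1% to 1% and 6 to 24 extra readings in ill participants only, the artefact is about 0.1 to 1.7 cases at 31 per arm, an apparent relative reduction of about 5% to 17%. When fever follows illness at 1% per reading, the relative reduction moves only from 49.2% to between 50.4% and 52.7%. These sizes rest on assumed reading counts and probabilities, independent readings, and the plan's symptomatic-infection rates as a stand-in for illness.

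A reader might conclude that the rule can create a vaccine effect. Under this mechanism it cannot, because the artefact is zero when illness is equal in both arms. Nor can it reach the primary family or any secondary efficacy endpoint, none of which uses measured temperature.

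**What to change.** In Sections 8.8 and 10.6.2, and as a derivation rule in the SAP before it is signed:

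1. For the efficacy summary, derive febrile illness only from readings scheduled in the Schedule of Activities, from the last Day 0 assessment to planned Day +12. The start matches the other tertiary symptom endpoints in Section 3. The fixed end is needed because those endpoints run to discharge, which can be later for participants who are more ill.
2. Keep the present any-reading rule as a sensitivity analysis, and report the number of temperature readings by arm beside both results.
3. Leave unscheduled readings in the safety data. Monitoring itself does not change.
4. Reconcile Section 8.8, which allows two routes, with Appendix 10.4, which treats temperatures outside reactogenicity monitoring as tympanic. Record the route with each reading.

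The cost is a few lines of wording, one derivation rule, one count by arm and a route field if none exists. The small downside is that a true fever seen only at an unscheduled or post-Day 12 reading would appear in the sensitivity analysis and the safety data, but not in the main febrile illness summary.

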8.9. Electrocardiogram

Study specific normal ranges are provided in [Appendix 10.4](#).

Twelve-lead ECGs will be obtained to evaluate the electrical activity of the heart. ECGs will be read on site by an appropriately qualified Investigator. Wherever possible the same Investigator will review subsequent ECGs from the same participant for the assessment of any change from baseline.

Any changes from baseline during the study will be assessed for their clinical significance. Clinically significant changes will be reported as AEs. The PI or delegate will assess non-clinically significant changes to determine whether they should be recorded.

8.10. Lung Function

Spirometry will be performed according to hVIVO's procedures. Height at screening will be used as the baseline measurement for all spirometry assessments.

Spirometry should meet the ATS/ERS guidelines criteria (Miller et al. 2005). For FEV₁ and FVC, the highest value from a minimum of 3 technically satisfactory attempts will be considered. For FEV₁ and FVC the highest and the second highest value difference should not exceed more than 150 mL or 5% (whichever is greater). If the difference is larger, up to 8 technically acceptable measurements will be made with repeatability assessed after each additional attempt. If after 8 technically acceptable attempts the difference remains greater than 150 mL or 5% (whichever is greater) the highest values will be reported, and an operator comment will be made to the source data. FEV₁ and FVC will be assessed and reported as the highest values regardless of curve.

Predicted values will be calculated according to the formula of the European Coal and Steel Community (ECCS).

Spirometry may be repeated at any time in the event of respiratory signs or symptoms (repeated coughing, bradypnoea, tachypnoea, rales and rhonchi) or respiratory difficulties.

8.11. Participant Diary Cards

8.11.1. Vaccination Diary Cards

Participants will be provided with a VDC, thermometer and calliper/ruler to measure and record local reactions and systemic events (including body temperature), for 7 days post-vaccination ([Appendix 10.3](#)). The diary card includes instructions on how to capture the data. Study site personnel are responsible for providing training for diary completion to avoid missing or incorrect data. Grading scales to assess severity of the symptoms are described in ([Appendix 10.3](#)).

Diary cards will be distributed on the day of vaccination (Day-28 (± 3 days)). Study site personnel will review the cards during the post vaccination visits (1 day and 7 days post-vaccination).

8.11.2. Symptom Diary Cards

Participants will report and assess the severity of any challenge virus-related signs and symptoms three times/day during quarantine, at the same time each day (± 1 hour), using the hVIVO Symptom Diary Card. This information will be collected using a paper form.

The following symptoms in the 13-item symptom questionnaire will be graded on a scale of 0-3 (grade 0: No symptoms; grade 1: just noticeable; grade 2: clearly bothersome from time to time but does not interfere with me doing my normal daily activities; grade 3: Quite bothersome most or all of the time, and it stops me participating in activities): Shortness of Breath and Wheeze have an additional grade 4: Symptoms at rest

- Runny nose
- Stuffy nose
- Sneezing
- Sore throat
- Earache
- Malaise/tiredness
- Headache
- Muscle and/or joint ache
- Chilliness/Feverishness
- Cough
- Chest tightness
- Shortness of breath
- Wheeze

Additional to the categorical symptom diary card, a Visual Analogue Scale diary card using a 100 mm scale, with the same symptoms, will be completed by the participants.

Participant cold perception questions

Two additional cold-related questions will be answered by the participant each morning. The first question asks whether the participant's perception of whether they have a cold or not, the second asks the participant's perception of improvement/worsening of the cold.

1. Do you have a cold: Yes/No

If the participant selects Yes to having a cold, then the second 7-point Likert scale "global change since yesterday" question is completed by the participant, as below.

2. **Compared to yesterday**, I feel that my cold is:

- Very much better
- Somewhat better
- A little better
- The same
- A little worse
- Somewhat worse
- Very much worse

